6. TREATMENTS

The following is a list of the study treatment abbreviations that will be used in the TFLs.

For Safety outputs

Study Treatment Name	Treatment order in TFLs
Humalog	1
LY900014	2
Bolus Dose Administration Method	Method order in TFLs
Standard dual-wave	1
Standard single-wave	2
Rapid single-wave	3
Rapid dual-wave	4

Statistical analysis treatment names

Study Treatment Name	Treatment order in TFL
Humalog standard dual-wave	1
Humalog standard single-wave	2
Humalog rapid dual-wave	3
Humalog rapid single-wave	4
LY900014 standard dual-wave	5
LY900014 standard single-wave	6

LY900014 rapid dual-wave	7
LY900014 rapid single-wave	8

7. SAMPLE SIZE JUSTIFICATION

An initial 24 patients may be randomized in order that approximately 20 patients complete the study. Twenty completing patients will provide approximately 80% power to demonstrate a 25% decrease in the time to early half-maximal concentration (early 50% T_{max}) between LY900014 and Humalog. Testing will be done at an α -level of 0.1 with a 2-sided confidence interval (CI). The variability was estimated by analyzing internal Lilly data (CCI [REDACTED]) for LY900014 and Humalog administered on CSII therapy, resulting in approximately 35.9% coefficient of variation of within-patient variability for early 50% T_{max}. Patients who are randomized but drop out before completing assigned treatment may be replaced to ensure that approximately 20 patients complete the study (refer to Section 5.1).

8. DEFINITION OF ANALYSIS POPULATIONS

The “Safety” population will consist of all patients who received at least one dose of study drug, and have at least one postdose safety assessment.

The “PK” population for the statistical inference will consist of all patients who complete the study according to the sequence/treatment to which they are randomized. In addition, a sensitivity analysis will be performed on the population consisting of all patients who complete at least 1 MMTT and have measurable insulin lispro concentrations.

The “GD” population for the statistical inference will consist of all patients who complete the study according to the sequence/treatment to which they are randomized. In addition, a sensitivity analysis will be performed on the population consisting of all patients who complete at least 1 MMTT and have measurable GD concentrations.

All protocol deviations that occur during the study will be considered for their severity/impact and will be taken into consideration when patients are assigned to analysis populations.

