10.3. Statistical Analyses

Statistical analysis of this study will be the responsibility of Eli Lilly and Company.

Primary statistical analyses will be conducted on the set of patients receiving at least 1 dose of the study drug to which they are randomized. The populations for the PK or GD analyses are defined in more detail in Section 10.3.2.1 and Section 10.3.3.1, respectively. Supportive analyses will be conducted on the set of patients who complete the study according to the sequence/treatment to which they are randomized. Safety analyses will be conducted on the set of patients receiving at least 1 dose of the study drug to which they are randomized and have at least 1 postdose safety assessment, regardless of whether or not they complete all protocol requirements.

For all PK/GD analyses (only applicable for breakfast meal tests), Days 1 and 3 and Day 2 will be analyzed using 2 separate and independent statistical models, assuming no carryover effect of the bolus administration mode from Day 1 to Day 2 or from Day 2 to Day 3 (refer to Section 5.4).

The CGM analyses for lunch and dinner will be documented in the statistical analysis plan.

Any change to the data analysis methods described in the protocol will require an amendment only if it changes a principal feature of the protocol. Any other change to the data analysis methods described in the protocol and the justification for making the change will be described in the study results.

Additional exploratory analyses of the data may be conducted as deemed appropriate. Analyses will be fully detailed in the statistical analysis plan. Study results may be pooled with the results of other studies for population PK analysis purposes to avoid issues with posthoc analyses and incomplete disclosures of analyses. Analyses will be fully detailed in the clinical study report, synopsis, and/or manuscript.

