10.3.2. Pharmacokinetic Analyses

10.3.2.1. Pharmacokinetic Parameter Estimation

Patients who complete at least 1 MMTT and have measurable insulin lispro concentrations will be included in the analysis dataset for the PK analyses. Patients who did not keep identical insulin lispro doses for the MMTTs (Days 1 and 3) will be excluded from the PK analysis on the MMTT days. In addition, patients who did not keep identical insulin lispro doses for the high-glycemic index meal tests (Day 2) will be excluded from the PK analysis on the Day 2 meal test days.

PK analyses will be conducted using standard noncompartmental methods of analysis on a computer that meets or exceeds the minimum system requirements for these programs. It is possible that other validated equivalent PK software programs may be used if appropriate, warranted, and approved by global PK management. The version of any software used for the

analysis will be documented, and the program will meet the Lilly requirements of software validation.

Serum insulin lispro concentrations will be used to calculate several PK parameters, including time to maximum concentration (T_{max}), early 50% T_{max} , time to late half-maximal concentration (late 50% T_{max}), C_{max} , area under the plasma concentration versus time curve (AUC) from time 0 to 15 minutes postdose (AUC[0-15min]), AUC from time 0 to 30 minutes postdose (AUC[0-30min]), AUC from time 0 to 1 hour postdose (AUC[0-1h]), AUC from time 0 to the last recorded time (AUC[0- t_{last}]), and AUC from time 0 to 5 hours postdose (AUC[0-5h]).

These will be the key parameters for analysis; other parameters (that is, partial AUCs) may be calculated as deemed appropriate.

Although attempts will be made to adhere to the scheduled collection times (Section 2), it is recognized that situations arise that may compromise sample collection at the scheduled times. Parameters will be individually calculated for each patient based on actual collection times and presented by summary statistics.

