10.3.3. Glucodynamic Analyses

10.3.3.1. Glucodynamic Parameter Estimation

Patients who receive at least 1 dose of study drug and have evaluable GD data will be included in the analysis set for the GD analyses. Also, for Days 1 and 3 and Day 2, separately, patients who did not complete the entire test meal or had significant changes in nutrient consumption of the

test meal or dose changes during the breakfast test meal will be excluded from all the GD analyses.

Data will be analyzed for the patients during each MMTT. The change from baseline values (the average of -30, -15, and 0 minutes represented as the 0-hour time point) for each patient will be calculated. Incremental change from baseline glucose AUC values will be calculated during a 5-hour meal test. Partial AUCs may be calculated as deemed appropriate.

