9.3.2 Pharmacokinetic Statistical Inference

The “PK” population for the statistical inference is defined in Section 8.

Log-transformed insulin lispro T_{max}, early 50% T_{max}, late 50% T_{max}, C_{max}, t_{1/2}, and AUC estimates will be evaluated to estimate geometric means, ratios of geometric means of insulin lispro within LY900014 to Humalog by day and bolus administration mode, and the corresponding 90% CIs of the ratios.

The statistical model for the Day 1 and Day 3 breakfast meal tests will include treatment (4 combinations of treatment and bolus administration mode: LY900014 dual-wave, Humalog dual-wave, LY900014 single-wave, or Humalog single-wave), period, day (Day 1 or Day 3), and treatment-by-day interaction as fixed effects and patient as a random effect.

Example SAS code:

```
proc mixed data=pk;
  class patient treatment period day ;
  model logpk = treatment period day treatment*day / ddfm=kr;
  lsmeans trt*day;
  random patient / grp= treatment;
  repeated / grp= treatment;
run;
```

A separate analysis model will be used for the Day 2 breakfast meal test, including treatment (4 combinations of treatment and bolus administration mode: LY900014 rapid, LY900014 standard, Humalog rapid, or Humalog standard, all given as a single-wave bolus) and period as fixed effects and patient as a random effect.

Example SAS code:

```
proc mixed data=pk;
  class patient treatment period;
  model logpk = treatment period / ddfm=kr;
  random patient / grp= treatment;
  repeated / grp= treatment;
run;
```

For the primary inference, insulin lispro administered from LY900014 will be concluded to have a significantly decreased early 50% T_{max} relative to Humalog if the upper confidence bound of the 2-sided 90% CI of the ratio of geometric means of the early 50% T_{max} is <1 .

If possible, the above models will also be used to calculate the intra-patient and inter-patient variability of LY900014, however if convergence issues occur, then the model will be appropriately updated to account for these issues.

As a sensitivity analysis, early 50% T_{max} will be analyzed by day using the Wilcoxon signed-rank test. The difference in median early 50% T_{max} between LY900014 and Humalog and the 90% CIs for the difference will be presented.

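### SAP 8 makes study completers the inference population for PK and GD, including the primary early 50% Tmax test; Protocol 10.3 makes completers supportive, and the SAP does not identify the change

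*SAP*

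**What the plan says.** Protocol 10.3 sets the order of analyses: "Primary statistical analyses will be conducted on the set of patients receiving at least 1 dose of the study drug", and "Supportive analyses will be conducted on the set of patients who complete the study". The Synopsis repeats the first rule. Protocol 10.3 then refers to two sections for the detailed sets:

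- PK (Protocol 10.3.2.1): "Patients who complete at least 1 MMTT and have measurable insulin lispro concentrations will be included in the analysis dataset".
- GD (Protocol 10.3.3.1): "Patients who receive at least 1 dose of study drug and have evaluable GD data will be included in the analysis set".

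SAP 8 says, once for PK and once for GD, that the "population for the statistical inference will consist of all patients who complete the study according to the sequence/treatment to which they are randomized". A wider set becomes a sensitivity analysis. For PK it is the protocol's own PK set. For GD it is "all patients who complete at least 1 MMTT and have measurable GD concentrations".

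SAP 9.3.2, which holds the primary decision rule for early 50% Tmax, says that its "population for the statistical inference is defined in Section 8". SAP 9.4.1 makes the same reference for GD.

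Two rules govern departures from the protocol. SAP 3 says the SAP supersedes the protocol's statistics and that substantial differences will be identified. Protocol 10.3 requires an amendment only when a principal feature changes; for other changes, "the justification for making the change will be described in the study results".

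**The concern.** The two documents name different analyses as the one that decides the trial's stated success criterion. If the completer analysis and the wider analysis fell on opposite sides of an upper bound of 1, a reader of the protocol and a reader of the SAP would draw different conclusions.

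Completion is also a post-randomisation event. A patient who drops out after one, two or three periods has usable meal-test data, and a mixed model with patient as a random effect can use it. The completer set discards it from the primary test.

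The set is not sharply defined either. Protocol 5.1.1 keeps a patient in the study when a period with a catheter change cannot be repeated, and Protocol 5.1.1.3 treats some Day 2 tests as missing. Neither document says whether such a patient counts as a completer. SAP 8 lets protocol deviations influence who enters each population, while SAP 13 lists the statisticians as unblinded from randomisation. A set defined by recorded facts leaves less to judgement.

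**Working it through.** **Comparison of the sets**

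| | Protocol | SAP 8 |
|---|---|---|
| Primary PK | At least 1 MMTT, measurable lispro | Completers |
| Other PK | Completers (supportive) | At least 1 MMTT, measurable lispro (sensitivity) |
| Primary GD | At least 1 dose, evaluable GD data | Completers |
| Other GD | Completers (supportive) | At least 1 MMTT, measurable GD (sensitivity) |

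For PK this is an exact reversal. For GD it is close to one, but the SAP's wider set is not quite the protocol's set. No SAP section identifies the change.

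The SAP is also not consistent with itself. SAP 9.3.1 keeps the protocol's PK dataset rule. SAP 9.4.2 asks for the GD analysis to be repeated in completers, which is redundant if completers are already the GD inference set.

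**Inputs**

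- 20 completers, within-patient CV 35.9%, ratio 0.75, two-sided alpha 0.10 (SAP 7).
- 24 patients initially, at most 30, to obtain 20 completers (Protocol 5.2).
- Breakfast order by sequence on Days 1 and 3 (Protocol Table ITSC.5.1).

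**The plan's own figure**

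- Within-patient log SD = sqrt(ln(1 + 0.359²)) = 0.3482.
- SE of a same-mode LY900014/Humalog log ratio = 0.3482 × sqrt(2/20) = 0.1101.
- Effect = |ln 0.75| = 0.2877.
- Noncentral t power is 80.9% with 19 df. With the residual df of the four-period model, 80 − 20 − 3 − 3 = 54, it is 82.5%.

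The stated power of about 80% is reproduced.

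**Share outside the primary set**

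- Initial plan: 4/24 = 16.7%.
- Enrolment cap: 10/30 = 33.3%.

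These shares overstate the loss of precision, because the lost patients would have given only part of their data.

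**Precision recovered by using partial data**

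The calculation is generalised least squares with four treatments and four periods fixed, a random patient intercept, a common residual variance and one test per period. The documents give no between-patient log SD, so it is varied from 0 to 0.7. The reference is 20 balanced completers, SE 0.1101.

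| Non-completers added | Periods each | SE | Reduction |
|---|---|---|---|
| 4 (one per sequence) | 0 | 0.1101 | 0% |
| 4 | 1 | 0.1074–0.1096 | 2.4–0.5% |
| 4 | 2 | 0.1050–0.1061 | 4.7–3.7% |
| 4 | 3 | 0.1027–0.1034 | 6.7–6.1% |
| 10 (2 or 3 per sequence) | 3 | about 0.093–0.096 | 15.4–12.4% |

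For 4 non-completers with 3 periods each (SE about 0.103, about 60 df), power for a ratio of 0.75 is 86.8%, against 82.5% for completers alone.

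**Bias**

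Every full completer receives both insulins in both breakfast modes, so the comparison is within patient. Dropout would bias the completer estimate only if it were related to the patient's own LY900014/Humalog ratio. Protocol 3.2.1 reports no discontinuations for drug-related adverse events in earlier studies. The documents do not allow the size or direction of any bias to be derived.

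**The case against.** The strongest reply is that the documents' own rules largely cover this. The SAP supersedes the protocol's statistics, and Protocol 10.3 allows a lesser change to be justified in the study results. Both analyses are prespecified, the sample size is stated in completers, and replacement exists to secure 20 of them. On this view only a flagging sentence is missing. It stands that there is no protocol breach in the missing reason itself and that the harm is small. It does not follow that completers are the planned primary set: Protocol 10.1 uses the same recruitment target while Protocol 10.3 makes completers supportive.

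Second, the protocol's sets also depend on post-randomisation conditions: a completed meal test, measurable lispro, identical doses, and a finished meal for GD. That is correct. Restoring them reduces the conditioning but does not remove it.

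Third, 17% and 33% are not forecasts. The documents state no dropout rate, and the number excluded could be zero. That also stands.

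Fourth, the power figures come from a simpler model than the SAP's example code, which groups both the random and the residual terms by treatment and models Days 1 and 3 together. If the grouped random term means independent patient effects per treatment, then at a between-patient log SD of 0.35 power is about 57% for completers and about 62% with 4 non-completers of 3 periods each. The absolute power figures therefore belong to the simplified model. The relative gain in SE stays in the same range.

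**Conclusion.** The concern holds. SAP 8 reverses the protocol's order of analysis sets for PK, and nearly so for GD. The reversal reaches the primary early 50% Tmax test, and the SAP does not identify it although SAP 3 says it would. The leftover wording in SAP 9.3.1 and 9.4.2 still fits the protocol's order, so the SAP needs reconciling with itself as well.

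The consequence is modest. With 4 non-completers the completer restriction forgoes a 0 to 6.7% reduction in SE, and at most about 4 percentage points of power. At the enrolment cap, with 3 periods from each of 10 non-completers, the forgone reduction is 12–15%. These figures assume 20 completers with four full periods (a best case), equal variances, one test per period and a common patient intercept. No bias has been shown, and the trial is not invalidated. It should be fixed because it leaves open which analysis decides.

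**What to change.** Revise SAP 8 so that the protocol's sets are primary:

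- PK: patients with at least 1 completed MMTT and measurable insulin lispro.
- GD: patients with at least 1 dose and evaluable GD data.

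State that the mixed model uses all available periods, and make completers the supportive analysis. Align SAP 9.3.1, 9.3.2, 9.4.1 and 9.4.2 with this; the completer repeat in 9.4.2 then has a purpose. Leave the dose and meal exclusion rules as they are. A sentence that only flagged the change would satisfy SAP 3, but the primary test would remain conditioned on completion.

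The cost is SAP wording, to be settled before sign-off, which SAP 3 places ahead of first dosing. For PK only the order of two planned analyses changes. For GD the set definition also shifts slightly. The primary model will work with somewhat unbalanced data. No added patients, visits or samples are needed, and planned power with 20 completers does not fall.

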9. STATISTICAL METHODOLOGY

9.1 General

Data listings will be provided for all data that is databased. Summary statistics and statistical analysis will only be presented for data where detailed in this SAP. For continuous data, summary statistics will include the arithmetic mean, arithmetic standard deviation, median, min, max and N; for log-normal data (e.g. the PK parameters: AUCs and C_{max}) the geometric mean and geometric coefficient of variation (CV%) will also be presented. For categorical data, frequency count and percentages will be presented. Data listings will be provided for all patients up to the point of withdrawal, with any patients excluded from the relevant population

highlighted. Summary statistics and statistical analyses will generally only be performed for patients included in the relevant analysis population. For the calculation of summary statistics and statistical analysis, unrounded data will be used.

Mean change from baseline is the mean of all individual patients' change from baseline values. Each individual change from baseline will be calculated by subtracting the individual patient's baseline value from the value at the timepoint. The individual patient's change from baseline values will be used to calculate the mean change from baseline using a **CCI** [REDACTED].

Unless otherwise specified, testing for significance is all done at an α -level of 0.1 with 2-sided confidence intervals (CIs). Statistical significance will be claimed if the p-value of a test is less than 0.1.

Data analysis will be performed using **CC** [REDACTED].

9.2 Demographics and Patient Disposition

Patient disposition will be listed. The demographic variables age, sex, race/subrace, ethnicity, country of enrolment, site ID, body weight, height and body mass index will be summarized and listed. In addition, screening HbA1c, fasting blood glucose, total daily insulin dose at screening, bolus dose at randomization, basal dose at randomization, fasting C-peptide and duration of T1DM will be summarized and listed.

Alcohol consumption will be reported in the SDTMs in units of alcohol and will be converted to grams for the TFLs, where 1 unit is equal to 8 grams of pure alcohol.

9.3 Pharmacokinetic Assessment

9.3.1 Pharmacokinetic Parameter Estimation

Patients who complete at least 1 MMTT and have measurable insulin lispro concentrations will be included in the analysis dataset for the PK analyses. Patients who did not keep identical insulin lispro doses for the MMTTs (Days 1 and 3) will be excluded from the PK analysis on the MMTT days. In addition, patients who did not keep identical insulin lispro doses for the high-glycemic index meal tests (Day 2) will be excluded from the PK analysis on the Day 2 meal test days.

PK analyses will be conducted using standard noncompartmental methods of analysis on a computer that meets or exceeds the minimum system requirements for these programs. It is possible that other validated equivalent PK software programs may be used if appropriate, warranted, and approved by global PK management. The version of any software used for the analysis will be documented, and the program will meet the Lilly requirements of software validation.

Serum insulin lispro concentrations will be used to calculate several PK parameters, including time to maximum concentration (T_{max}), early 50% T_{max} , time to late half-maximal concentration (late 50% T_{max}), C_{max} , area under the plasma concentration versus time curve (AUC) from time 0

to 15 minutes postdose (AUC[0-15min]), AUC from time 0 to 30 minutes postdose (AUC[0-30min]), AUC from time 0 to 1 hour postdose (AUC[0-1h]), AUC from time 0 to the last recorded time (AUC[0-t_{last}]), AUC from time 0 to 5 hours postdose (AUC[0-5h]), change from baseline PK parameters such as change from baseline AUC (CFBLAUC[0-5], and CFBLAUC[0-∞]). These will be the key parameters for analysis; other parameters (that is, partial AUCs and CL/F) may be calculated as deemed appropriate.

Although attempts will be made to adhere to the scheduled collection times (Section 2) detailed in the protocol, it is recognized that situations arise that may compromise sample collection at the scheduled times. Parameters will be individually calculated for each patient based on actual collection times and presented by summary statistics.

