3. INTRODUCTION

This SAP has been developed after review of the Clinical Study Protocol (final version dated 19 November 2016 and amendment (a), dated 6 February 2017).

This SAP describes the planned analysis of the safety, tolerability, pharmacokinetic (PK) and glucodynamic (GD) data from this study. A detailed description of the planned TFLs to be presented in the clinical study report (CSR) is provided in the accompanying TFL shell document.

The intent of this document is to provide guidance for the statistical and PK analyses of data. In general, the analyses are based on information from the protocol, unless they have been modified by agreement between Eli Lilly and Company and CCI. A limited amount of information concerning this study (e.g., objectives, study design) is given to help the reader's interpretation. This SAP must be signed off prior to first patient administration for this study. When the SAP and TFL shells are agreed upon and finalized, they will serve as the template for this study's CSR.

This SAP supersedes the statistical considerations identified in the protocol; where considerations are substantially different, they will be so identified. If additional analyses are required to supplement the planned analyses described in this SAP, they may be performed and will be identified in the CSR. Any substantial deviations from this SAP will be agreed upon between Eli Lilly and Company and CCI and identified in the CSR. Any minor deviations from the TFLs may not be documented in the CSR.

This SAP is written with consideration of the recommendations outlined in the International Council on Harmonization (ICH) E9 Guideline entitled Guidance for Industry: Statistical Principles for Clinical Trials¹ and the ICH E3 Guideline entitled Guidance for Industry: Structure and Content of Clinical Study Reports².

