10. INTERIM ANALYSES

No interim analyses are planned for this study. If an unplanned interim analysis is deemed necessary, the Lilly clinical pharmacologist, CRP, investigator, or designee will consult with the appropriate medical director or designee to determine if it is necessary to amend the protocol.

The Lilly clinical pharmacologist/CRP/Lilly study team is unblinded. Data may be accessed and analyzed while the trial is ongoing, but no changes to the study design are planned. The results may help Lilly expedite final delivery and enable planning of future studies. Information that may unblind the study during the analyses will not be reported to the study site until the study has been unblinded. An assessment committee will not be formed.

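### SAP 9.3.2 puts t1/2 in the inference list although basal lispro runs through every breakfast test and no basal correction or terminal-slope rule is given

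*SAP*

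**What the plan says.** **Basal delivery.** Protocol Section 2 (treatment administration row) has the assigned insulin delivered continuously as basal and, in addition, as a meal bolus. SAP 5 sets one hourly basal rate during the breakfast tests, from about 6 AM to 2 PM. The assay (Protocol 9.5.1) is specific for lispro. Basal and bolus are both lispro, so each measured value is their sum.

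**Parameters.** SAP 9.3.1 states: "Serum insulin lispro concentrations will be used to calculate several PK parameters, including time to maximum concentration". It then adds "change from baseline PK parameters such as change from baseline AUC", over 0-5 hours and to infinity. It does not mention t1/2.

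**Inference.** SAP 9.3.2 states: "C_{max}, t_{1/2}, and AUC estimates will be evaluated to estimate geometric means", with LY900014/Humalog ratios and 90% intervals by day and bolus mode. SAP 2 defines t1/2 through the terminal rate constant. The matching list in Protocol 10.3.2.2 does not contain it.

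**Baseline.** SAP 9.1 states: "Each individual change from baseline will be calculated by subtracting" the patient's own baseline. No section says which lispro sample that is. Baselines are defined for vital signs (9.5.4), glucose (9.4.1) and CGM (9.5.10).

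**Timing.** The last lispro samples are at 150, 180, 240 and 300 minutes. A dual-wave bolus delivers half its dose over 3 hours.

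**The concern.** A half-life from the terminal log slope assumes that concentration decays toward zero. Here it decays toward a plateau that the pump maintains. The fitted slope then depends on how little bolus insulin is left relative to basal. An insulin that clears its bolus sooner sits closer to the plateau at 180 to 300 minutes, has a flatter slope, and appears to have the longer half-life.

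At stake is a reported ratio with a 90% interval that could point the wrong way on how quickly LY900014 leaves the circulation. On a nearly flat tail, assay error can also make the fitted slope positive. The log of t1/2 is then undefined and the value drops out, more readily for the insulin that reaches the plateau sooner.

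The baseline-corrected AUC to infinity needs the same terminal slope. Neither corrected AUC can be computed uniquely until the baseline sample is named.

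**Working it through.** **1. The plan's own figure.** SAP 7 gives 20 completers, ratio 0.75, two-sided alpha 0.1 and "35.9% coefficient of variation of within-patient variability for early 50"% Tmax.
- Log SD = sqrt(ln(1 + 0.359²)) = 0.348.
- SE = 0.348 × sqrt(2/20) = 0.110.
- |ln 0.75| / SE = 0.288 / 0.110 = 2.61.
- Power with 19 df = 81%, against a stated 80% or so. The figure reproduces.

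**2. Algebra.** Let C(t) = B + d(t), with B the basal level and d(t) = A·exp(-λt) the bolus remainder. The slope of ln C is -λ·f, where f = d/(B + d) is the bolus share of the total. The apparent half-life at time t is the true one divided by f. It grows without limit as the bolus clears.

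**3. Illustrative model.** The documents give no basal level, so every pharmacokinetic input is assumed:
- two absorption steps, and elimination 2/h (half-life 60 × 0.693/2 = 21 min);
- basal amount = hourly rate/2;
- bolus (U) and basal (U/h) pairs (6, 0.5), (8, 0.8), (10, 1.0), (6, 1.2), (10, 1.5);
- LY900014 either absorbed faster (3.6/h against 2.2/h) or with a shorter lag (2 against 9 min, both 3.0/h).

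Delivery speed (1.5 U/min) and sampling times are the protocol's. t1/2 is the log-linear fit at 180, 240 and 300 min. With three equally spaced points the slope is (ln C300 - ln C180)/2 per hour.

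**4. One case by hand.** Single-wave, 6 U, 0.5 U/h, faster absorption, with B = 0.25 U. The bolus remainder is in multiples of B:

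| | d(180) | d(300) | Corrected t1/2 | Raw t1/2 |
|---|---|---|---|---|
| Humalog | 0.9253 | 0.0370 | 0.693 / [ln(0.9253/0.0370)/2] = 0.431 h = 26 min | 0.693 / [ln(1.9253/1.0370)/2] = 2.24 h = 134 min |
| LY900014 | 0.3070 | 0.0059 | 0.693 / [ln(0.3070/0.0059)/2] = 0.351 h = 21 min | 0.693 / [ln(1.3070/1.0059)/2] = 5.29 h = 318 min |

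The LY900014/Humalog ratio is 21/26 = 0.81 corrected and 318/134 = 2.4 raw.

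**5. All single-wave cases.** Corrected t1/2 is 21-26 min; raw is about 135-710 min. With faster absorption the ratio goes from 0.81 to 2.4-2.6. With shorter lag it goes from 0.99 to about 1.2.

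**6. Dual-wave cases.** The immediate part takes 2-3 min (3-5 U at 1.5 U/min). Delivery therefore ends at 180 min, or at 182-183 min if the square wave follows it. Only the 240 and 300 min samples clearly come later. Fitted over 180-300 min, t1/2 is about 34-50 min corrected and 85-161 min raw, against the assumed 21. Subtraction alone does not repair it. The direction does not reverse here, but raw ratios move toward 1 (0.68 becomes 0.87-0.92 with faster absorption).

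**7. A second, simpler model.** This is one-compartment absorption, with basal at 30% of the bolus peak. Apparent t1/2 goes from 39 to 193 min for the reference and from 35 to 318 min for the test curve. The ratio goes from 35/39 = 0.90 to 318/193 = 1.65, again a reversal.

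**The case against.** **A competent analyst would see the plateau and subtract it.** Perhaps, and the separate output shells, which were not available, might say so. But the SAP neither instructs it nor names the baseline, and it adds t1/2 to a list where the protocol does not have it.

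**The sizes are assumed.** They are, and the reversal appears only in single-wave tests. The lengthening does not depend on the assumed values: with any positive basal level f is below 1, so raw t1/2 is too long.

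**A tempting stronger reading** is that the primary endpoint itself is undefined. Basal lispro also sits under early 50% Tmax, on which "insulin lispro administered from LY900014 will be concluded to have a significantly decreased early 50"% Tmax, and 9.3.1 does not write uncorrected beside it. The documents do not support that reading. SAP 2 defines Cmax as an observed maximum, SAP 12.1 reports it as received, and 9.3.1 names corrected quantities separately as change from baseline. Early 50% Tmax, Cmax and the ordinary AUCs therefore read as uncorrected. Meal-test doses must be identical across periods (Protocol 5.5), and ratios are taken within bolus mode. Much of the basal-to-bolus difference between patients and modes therefore stays out of the insulin comparison. Correction is not clearly better either: in the same model the early 50% Tmax ratio shifts one way with faster absorption and the other way with shorter lag. Explicit labels would help; their absence is not an error in the primary test.

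**Conclusion.** The point holds for t1/2 and, through the same slope, for the baseline-corrected AUC to infinity. Uncorrected t1/2 in this design is not a half-life. In the assumed model it is roughly five to more than thirty times too long in single-wave tests (134/26 = 5; 710/21 = 34), and the ordering of the insulins can reverse. For dual-wave tests the sampling schedule does not support a terminal slope even after subtraction. The missing lispro baseline is a smaller gap with a simple repair.

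The ranges rest on assumed pharmacokinetic inputs. The qualitative conclusion rests only on the continuing basal infusion. A reader might infer a biased primary test, an inflated type I error or an overstated power. None of these follows, and the stated power reproduces.

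**What to change.** 1. **t1/2.** Delete it from the inference list in SAP 9.3.2, which restores agreement with Protocol 10.3.2.2. Alternatively, keep it for single-wave tests only, from baseline-subtracted lispro, with written rules: minimum number of points, start after delivery ends, and handling of values at or below baseline. Do not infer on it for dual-wave tests.
2. **Baseline-corrected AUC to infinity.** Apply the same limits, and rely on the 0-5 hour version for dual-wave tests.
3. **Baseline.** In SAP 9.3.1, name the mean of that test day's -15 and 0 minute samples.
4. **Labels.** Mark early 50% Tmax, Cmax and the AUCs as uncorrected for inference. A baseline-subtracted early 50% Tmax could be added as supportive.

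Settle this at sign-off. The SAP states "This SAP must be signed off prior to first patient administration for this study", and the sponsor team is unblinded: "Data may be accessed and analyzed while the trial is ongoing".

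**Cost.** t1/2 is lost or restricted, and one derivation step is added. No new samples are needed.

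**Limit of the single-wave option.** In the case worked by hand, the bolus remainder at 300 minutes is 3.7% of basal for Humalog and 0.6% for LY900014. If the basal rate changes by an assumed 20% at 6 AM, the model has completed 72-87% of the change at -15 minutes and 80-92% at time 0. The average shortfall is 10.5-24%. Times 20%, that is 2-5% of the old rate, or up to 4.8/0.8 = 6% of B after a decrease. This is as large as the signal. A test starting after 9 AM also has its 300 minute sample after the 2 PM end of the single-rate window. Deletion is therefore the simpler choice.
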